Assent from a subject will be obtained if they are aged 10 to 17 years along with informed consent from the eligible subject's parent or legal guardian. Informed consent will be obtained from subjects aged 18 years or older. All informed consent/assent discussions will take place in a private room and be documented according to the Pediatric Research Office's 'Informed Consent Process Cover Sheet'. Potential subjects and family members will be given as much time as necessary to determine if they would like to participate in the study. No study team member will be present during this period to minimize any possible coercion.

After informed consent is obtained the subject will be assigned a unique ‘Subject Identification Number.’ This number will consist of ‘VCUFP##’, where the first subject will be ‘VCUFP01’, the second ‘VCUFP02’, and so forth. This unique identifier will be used instead of the subject’s name, birth date, etc., to identify the subject for all study records and data.

After Subject Identification Number assignment is performed, randomization will occur. The study team will use the website www.randomization.com to randomize 30 study conditions (15 experimental and 15 control). The Study Coordinator will follow the randomization table chronologically as new subjects are consented.

This study is designed to accommodate 30 subjects (15 subjects per group) (Table 1). The study population will be determined from previously diagnosed CF patients who receive their CF care at CHoR and Virginia Commonwealth University. Subjects will be aged 10 years and older who are experiencing a CF exacerbation that requires hospital admission and therapy.

Table 1
STUDY DESIGN

Study Group	Assigned Intervention	Total Number of Subjects
Control Therapy	Low-Flow, 5 LPM (via Optiflow™ cannula) Heated (34°C), humidified air	15
Experimental Therapy	High-Flow, 20 LPM (via Optiflow™ cannula) Heated (34°C), humidified air	15

If a subject requests to withdraw from the study at any point, they are asked to inform the study doctor. Withdrawal from the study will not affect standard treatment the subject will receive for their CF exacerbation or ongoing treatment they may require. Upon withdrawal, the subject will forfeit any compensation for study participation.

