- Has any contraindications to HHNC as listed below:
 - Maxillofacial trauma
 - Complete nasal obstruction
 - Presence of suspected base of skull fracture
- Any contraindication that applies to CPAP/ NIV therapy

STUDY PROCEDURES

The study requires clinical observations and overnight intervention therapy for/up to the first 5 nights of hospitalization. The study procedures to be performed on/by each subject enrolled in the study are outlined in Table 2.

Table 2
STUDY PROCEDURES

Time point	Procedure/Assessment
SCREENING (Day 0) (In CF Clinic or within 24 hours of hospital admission)	
Admission into the Children's Hospital of Richmond or MCV Hospital for adult subjects (hospital).Introduction to study and review the study procedures/study device with the study coordinator and/or study doctorVerification of inclusion/exclusion criteria and signing of Informed Consent Document.Assignment of the unique Subject Identification NumberReview of medical history and treatment recordsBaseline tests (as part of standard of care as medically indicated)Completion of the Leeds Sleep Evaluation Questionnaire (LSEQ) by subject.Completion of the CF-specific health related quality of life survey (Cystic Fibrosis Questionnaire – Revised (CFQ-R) by subject.Completion of the Sino-Nasal Outcome Test (SNOT-20) by subject.Sputum sample collection (if possible)Randomization to intervention - either: 'Control Therapy' (Low Flow, heated and humidified air delivered at 5 LPM via Optiflow™ cannula and AIRVO™2 device) or 'Experimental Therapy' (High-Flow, heated and humidified air delivered at 20 LPM via Optiflow™ cannula and AIRVO™2 device)

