DISCHARGE Day 6 (AM)* (*or earlier if discharged prior to 5 days of treatment)	
 The device will be turned off (unless the subject has wakened earlier), in which case the subject can turn off the device when they wake. Sputum sample will be collected (where possible) or collection of previously produced sputum to research laboratory by study coordinator by 10:00 AM. Subject will remove Actiwatch® 2 and Study Coordinator will download Actiwatch® 2 data Completion of the Leeds Sleep Evaluation Questionnaire (LSEQ) by subject Completion of the CF-specific health related quality of life survey (Cystic Fibrosis Questionnaire – Revised (CFQ-R) by subject Completion of the Sino-Nasal Outcome Test (SNOT-20) by subject Completion of the device comfort survey (VAS Score) by subject. The study coordinator will collect the device log, and review the previous night's medical records (including any test results or medication dispensed). A follow-up appointment in the CF clinic will be scheduled according to the study doctor's recommendations (as part of standard care). The subject will be reminded to call the study coordinator or the study doctor if there are any new problems, questions or concerns once discharged from the hospital.
Clinical Follow-up Appointment	
 The study coordinator and/or the study doctor will review the medical history and treatment records. Baseline tests (as part of standard of care as medically indicated) Completion of the Leeds Sleep Evaluation Questionnaire (LSEQ) by subject Completion of the CF-specific health related quality of life survey (Cystic Fibrosis Questionnaire – Revised (CFQ-R) by subject Completion of the Sino-Nasal Outcome Test (SNOT-20) by subject Sputum sample collection (if possible). The sputum will be delivered to the research laboratory by the Study Coordinator Study compensation

DATA HANDLING AND RECORD KEEPING

Power Calculation

No studies have evaluated the effect of high-flow HHNC therapy to improve sinopulmonary symptoms in CF. Thus, the current study is designed as a pilot study that is likely to be underpowered to reach significance.

Electronic Database Capture

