Statistical analysis of data will be performed using the JMP Pro 10 statistics package (SAS Institute, Cary, NC). Normality of data distribution will be visually checked and normally distributed data will be compared using two-tailed t-test and ANOVA. A $p < 0.05$ will be considered statistically significant. All results will be presented as means + the standard error of the mean.

QUALITATIVE EVALUATION

One sleep and three separate quality of life evaluations will be administered at various time-points according to Table 2 - Study Procedures. The information provided by the questionnaires will be transposed into the REDCap database by the study coordinator. All paper documents will be de-identified, the only identifier is the Subject Identification Number, which is kept in a locked cabinet, in the study coordinator's locked office.

Leeds Sleep Evaluation Questionnaire (LSEQ)

The Leeds Sleep Evaluation Questionnaire (LSEQ) is a 10-item, subjective, self-report, 5-10 minute paper and pencil measure designed to assess changes in sleep quality over the course of a psychopharmacological treatment intervention. The scale evaluates four domains: ease of initiating sleep, quality of sleep, ease of waking and behavior following wakefulness using paper and pencil. Developers initially validated the LSEQ in individuals aged 18-49 years. In the evaluation "initiating sleep" and the "quality of sleep" factors were correlated with one another while "awakening from sleep" and "behavior following wakefulness" factors were also correlated. Of the validated scales available to use for this study the LSEQ appears to be the most appropriate given the study being conducted.

Cystic Fibrosis Questionnaire-Revised (CFQ-R)

The Cystic Fibrosis Questionnaire-Revised (CFQ-R) is health-related quality of life (HRQoL) measure for children, adolescents and adults with CF. Initially it was developed through interviews with CF patients and healthcare providers and various focus groups and has since undergone comprehensive reliability and validity testing. This revised questionnaire is one of the most widely used HRQoL tests for CF. The CFQ-R measures how well an individual functions in a variety of domains, including Physical Functioning, Vitality, Health Perceptions, Respiratory Symptoms, Treatment Burden, Role Functioning, Emotional Functioning, and Social Functioning. This questionnaire is written for the intended age group in regards to language and length of questionnaire.

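### One unstratified 15:15 list spans ages 10 and up and the analysis names no age term, so a chance age split can bias a given arm comparison and costs precision, mainly for sleep duration

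*Combined protocol and SAP*

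**What the plan says.** **Allocation.** Under Study Design: "The study team will use the website www.randomization.com to randomize 30 study conditions (15 experimental and 15 control". The same section adds: "The Study Coordinator will follow the randomization table chronologically as new subjects are consented". No strata or blocks are named.

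**Population.** "Subjects will be aged 10 years and older who are experiencing a CF exacerbation that requires hospital admission and therapy". There is no upper age limit and no quota of children or adults. The consent procedure in the same section already separates subjects aged 10 to 17 (assent plus parental consent) from those aged 18 or older.

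**Hospital.** The Screening row of Table 2 admits subjects to the children's hospital or to "MCV Hospital for adult subjects".

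**Questionnaires.** Of the CFQ-R the plan says: "This questionnaire is written for the intended age group in regards to language and length of questionnaire". Of the LSEQ it says: "Developers initially validated the LSEQ in individuals aged 18-49 years".

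**Actigraphy.** Sleep duration by Actiwatch is a secondary objective. Table 2 mentions the watch only in the Discharge row: "Subject will remove Actiwatch® 2 and Study Coordinator will download Actiwatch® 2 data". The row labelled Baseline (Day 1) begins with the humidifier being switched off in the morning, so the preceding night was already on treatment.

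**Analysis.** The Data Analysis section names a two-tailed t-test and ANOVA at p < 0.05. It lists no age, hospital or baseline term.

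**The concern.** Age group is known before randomization and could affect several outcomes. It goes with the admitting hospital and with the form of the CFQ-R, and it may go with how long a subject sleeps. With 15 subjects per arm, the numbers of children in the two arms can differ noticeably by chance. If they do, and the comparison ignores age, part of the child-adult difference is read as an effect of flow rate. If they do not, the age difference stays in the error term and widens the confidence interval.

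Sleep duration is the most exposed outcome. No actigraphy is scheduled before the device is in use, so neither a change score nor adjustment for a subject's own baseline can absorb an uneven split. FEV1 is defined as a change from admission, and CFQ-R, SNOT-20 and LSEQ are completed on Day 0 (sputum too, where obtainable). Analysed as change, these are partly protected from age differences in level, though not from different rates of change.

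**Working it through.** The plan gives no sample-size derivation, SD or expected age mix, so there is no figure to reproduce beyond 15 + 15 = 30.

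**Inputs from the plan:** 30 subjects, 15 per arm, one list, two-sided 0.05.

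**Assumptions not in the plan:** K = 10 to 20 children among 30; children sleep 1.0 h longer than adults; within-age-group SD of nightly sleep 0.8 to 2.0 h.

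**1. Chance of an uneven split.** The number of children in one arm, k, is hypergeometric (30 subjects, K children, 15 drawn). The arms differ by |2k − K| children, which is even when K is even and odd when K is odd.

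| K | P(differ by ≥ 4) | P(differ by ≥ 5) |
|---|---|---|
| 10 or 20 | 24.5% | 5.0% |
| 11 or 19 | 12.8% | 12.8% |
| 12 or 18 | 26.4% | 6.0% |
| 13 or 17 | 13.9% | 13.9% |
| 14 or 16 | 27.2% | 6.6% |
| 15 | 14.3% | 14.3% |

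The ranges are therefore 13% to 27% for 4 or more, and 5% to 14% for 5 or more.

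**2. Shift in the arm difference.** Shift = (difference in number of children / 15) × child-adult gap. For a 10:5 split and a 1.0 h gap: (5/15) × 60 min = 20 min. This needs a difference of 5, so the 5% to 14% column applies to it, not the 13% to 27% column.

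**3. Size against sampling error.** The standard error of the arm difference, with age removed, is SD × √(2/15). At SD 1.2 h this is 72 min × 0.365 = 26 min.

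**4. False-positive rate given a 10:5 split, and variance inflation.** The first comes from simulating the planned t-test with no treatment effect. The second is 1 + q(1 − q) × gap² / SD², with q = K/30 = 0.5, so 1 + 0.25 / SD² for a 1.0 h gap.

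| SD (h) | Standard error (min) | False-positive rate given 10:5 | Variance inflation |
|---|---|---|---|
| 0.8 | 18 | 12% | 39% |
| 1.2 | 26 | 8.6% | 17% |
| 1.6 | 35 | 7.3% | 10% |
| 2.0 | 44 | 6% | 6% |

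In terms of subjects, 17% inflation means that an unadjusted comparison would need about 30 × 1.17 = 35 subjects to match the precision of an age-adjusted one with 30.

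**5. Averaged over all splits.** Weighting the simulated rates by the hypergeometric probabilities returns about 5%. Balanced splits reject too rarely and uneven ones too often, and the two offset each other.

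**The case against.** The strongest reply is that randomization is valid as it stands. Overall type I error is near 5%, and in a pilot that the plan itself expects to be underpowered, a 20-minute shift is smaller than the standard error of about 26 minutes (SD 1.2 h). That stands in large part. A reader might infer that an age split would drive the result or that the test is invalid; the figures support neither. Only at the small end of the SD range (0.8 h, standard error 18 min) does the shift exceed the standard error, and it still needs a split with a 5% to 14% chance.

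Four other stronger readings also go beyond the documents:

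- **All questionnaires are age-specific.** Only the CFQ-R is described so, and its age bands are not given. The LSEQ validation range also excludes adults over 49, whom a cut at 18 does not separate.
- **Hospital changes at exactly 18.** That age is used for consent; the admission age for the adult hospital is not stated. The plan also calls the study single-center and gives all nursing staff the same instruction on cannula wear.
- **The primary endpoints are compromised.** They are changes, and FEV1 is also percent predicted.
- **The plan rules out an age term.** It names none, but lists no ANOVA factors at all.

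It is also fair to say that stratified blocks in a 30-subject pilot are a matter of judgement. Totals may miss 15:15 slightly, and the ends of blocks become easier to guess. What the objection does not answer is why a variable already in hand should be left out of the comparison.

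**Conclusion.** The point holds as one of conditional bias and lost precision, chiefly for actigraphic sleep duration, a secondary outcome. An uneven split is not rare: 13% to 27% for a difference of 4 or more children. The worked 20-minute shift belongs to the less common difference of 5 or more. Given that shift, the false-positive rate is 12% to 6%; on average over splits, ignoring age inflates the variance by 39% to 6%. All of these sizes rest on the assumed age mix, the 1.0 h gap and the SD range; a smaller gap would reduce the shift, the conditional error and the inflation together. Because no ANOVA factors are listed, the defect is an omission from the written plan that can be closed before analysis.

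**What to change.** Prespecify age group (10-17 v 18 or older, already established at consent) as a factor in the arm comparisons, sleep duration above all. It costs 1 of about 28 degrees of freedom and needs no new data. Show CFQ-R and LSEQ results by age group descriptively beside the pooled result. State in Table 2 when the Actiwatch is fitted, so that a reader can tell whether any pre-device recording exists.

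Stratifying the list by age group is optional, and only if randomization has not begun. Its costs are a second list, totals that may miss 15:15 by one or two, and slightly greater predictability if blocks are used. If subjects are already randomized, keep the list and add only the factor.

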Study subjects may be involuntarily removed from the study if the study doctor believes that they are not complying with the study protocol and/or the study doctor believes it is in the best interest of the subject to stop participation.

Study devices/equipment

The experimental therapy will be administered using Optiflow™ nasal cannula with the AIRVO™2 humidifier. The AIRVO™2 device will heat and humidify ambient air and the Optiflow™ nasal cannula will deliver the heated (approximately 34°C) and humidified air via the nares at a flow of 20 LPM.

Fisher & Paykel Healthcare manufactures the Optiflow™ nasal cannula and the AIRVO™2 device. The Optiflow™ nasal cannula and AIRVO™2 device are being provided by Fisher & Paykel Healthcare for the study with no cost to the study subject. In addition, the subject will not be subjected to any further costs associated with the study. The study devices will only be available for use by the subjects that are enrolled in the study. The subject will be required to return the study device at the conclusion of the subject’s study involvement, or when the subject is discharged from the hospital (whichever occurs first).

The control therapy will be administered using Optiflow™ nasal cannula with the AIRVO™2 device. The nasal cannula will deliver heated (approximately 34°C) and humidified air into the subject’s nares at a flow of 5 LPM. This aims to mask the experimental and control therapy from the subjects and investigators.

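### A subject who asks to withdraw loses all compensation, with no pro-rating and no stated exception for device-related harm, and payment is listed only at an undated final visit

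*Combined protocol and SAP*

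**What the plan says.** The withdrawal paragraph in Study Design, just after Table 1, opens with the subject's own request to leave: "If a subject requests to withdraw from the study at any point, they are asked to inform the study doctor". It protects clinical care: "Withdrawal from the study will not affect standard treatment the subject will receive for their CF exacerbation or ongoing treatment they may require". It then sets the financial consequence: "Upon withdrawal, the subject will forfeit any compensation for study participation".

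The next paragraph covers removal by the study doctor, either for non-compliance or where "the study doctor believes it is in the best interest of the subject to stop participation". It does not mention compensation.

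Table 2 (Study Procedures) lists compensation only in its last row, the Clinical Follow-up Appointment. There it runs on from the sputum item: "The sputum will be delivered to the research laboratory by the Study Coordinator Study compensation" (the last two words are a separate list entry). The Discharge row sets the timing of that visit: "A follow-up appointment in the CF clinic will be scheduled according to the study doctor's recommendations".

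Two passages on consent in Study Design give context. Minors take part: "Assent from a subject will be obtained if they are aged 10 to 17 years", together with consent from a parent or guardian. While the family decides, "No study team member will be present during this period to minimize any possible coercion".

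**The concern.** Payment that is lost in full on withdrawal makes leaving costly, and the cost is greatest for a subject who has already done most of the work. The subjects here are inpatients with an acute exacerbation, some of them children. They wear a nasal device for up to five nights under nursing checks and may be woken to have the cannula repositioned. The eligibility criteria exclude recent nasal bleeding and recent pressure headaches that needed therapy, so the protocol itself recognises that some people may be poorly suited to the device. It is foreseeable that some subjects will want to stop.

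Two things are at stake. The first is whether withdrawal is as free as the consent process intends. The second is data. Once payment is gone, a subject who has left has no paid reason to give the remaining sputum samples and questionnaires, and sputum properties are among the primary endpoints.

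**Working it through.** There is no figure to reproduce. The documents give no payment amount and no expected withdrawal rate, so the check is a reading of the relevant text side by side.

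1. **Trigger.** Forfeiture sits in the paragraph on subject-requested withdrawal and applies at any point, from consent up to the final visit.
2. **Extent.** The sentence covers any compensation. No part-payment for completed assessments is described.
3. **Reason for leaving.** The paragraph does not distinguish reasons. No exception is stated for discomfort or an adverse effect. The only protection given is for standard and ongoing treatment, which is not payment.
4. **Timing.** Table 2 has five time points: Screening (Day 0), Day 1, Days 2 to 5, Discharge (Day 6 or earlier) and the follow-up appointment. Compensation is listed at the fifth only. Device use lasts at most five nights, but the follow-up visit has no fixed date. The period in which payment can be lost is therefore longer than the treatment period and has no stated end.
5. **Removal by the study doctor.** This is a separate route, and its effect on payment is not stated.
6. **Stopping the device.** The protocol does not separate this from leaving the study. A subject who stops wearing the cannula could be classed in three ways, with different results for payment:
   - as having withdrawn: payment forfeited;
   - as non-compliant and removed: payment not stated;
   - as still in the study but off the device: nothing says payment is lost.
7. **Assessments exposed.** For a subject who stops after Day 1, Table 2 still has the Discharge sputum sample, LSEQ, CFQ-R, SNOT-20 and comfort VAS, then the follow-up sputum sample, LSEQ, CFQ-R and SNOT-20. The protocol does not say whether these are sought after withdrawal. With 15 subjects per group, each subject without later data is 1/15 = 6.7% of an arm, and the Data Analysis section names no method for missing data. The 6.7% is the weight of one subject, not a forecast of how many will leave.

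Items 1 to 4 together establish the rule: all-or-nothing payment, listed at an undated last visit and lost on voluntary withdrawal with no stated exception. Items 5 and 6 are gaps in the text that the same amendment can close.

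**The case against.** The strongest case on the other side has five parts.

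- **Nothing is contradicted.** A reader might infer that forfeiture contradicts the protocol's own statement on coercion. It does not. That statement concerns the time when a potential subject and family decide whether to join, and it does not mention payment or later withdrawal. The two sit in tension in principle only. This objection stands.
- **Harm is not singled out, and there is another way out.** The rule does not target subjects who are harmed. The study doctor may remove a subject in that subject's best interest, and no forfeiture is stated for that route. Nor is stopping the device said to be withdrawal. This stands as a limit: the documents support saying that no exception is stated, but not that every subject stopped for harm loses payment.
- **Biased comfort data.** A reader might infer that subjects will under-report discomfort, more so in the less comfortable arm. The documents do not support this. Payment depends on not withdrawing, not on the comfort score, so a subject can record severe discomfort, stay in and be paid. No figure or direction by arm is available.
- **Payment on completion helps retention.** This is partly right. It gives subjects a reason to stay and so may preserve late data. It does nothing for a subject who has already left, and it gets retention by making exit costly.
- **The amount is unknown and payment is for the IRB.** The sum may be a token one, and removed consent pages may contain payment terms. IRB approval is required before the study starts. None of this alters the protocol sentence. If the consent form does pro-rate payment, it conflicts with that sentence and the two need reconciling.

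**Conclusion.** The concern holds in limited form. The protocol states total forfeiture on subject-requested withdrawal, without pro-rating and without an exception for device-related discomfort or harm. It lists compensation only at a final visit with no fixed date. In a study that takes inpatients from age 10, that is a financial penalty on leaving. It also removes any paid reason for a subject who withdraws early to supply Discharge and follow-up data.

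The rule applies to all 30 planned subjects. Its strength cannot be sized, because neither the amount nor the expected number of withdrawals is given. A reader might want to express the loss as the share of visits completed before leaving. The documents give no weighting of visits, and a subject who leaves between Day 6 and the clinic appointment has already finished with the device, so such a share would not measure a penalty for stopping because of harm.

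The conclusion assumes that the protocol sentence is applied as written. It changes no endpoint definition or planned test. Its bearing on the data is indirect, through who remains to be measured. It still merits an amendment, because the rule is stated outright and is cheap to replace.

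**What to change.** Replace the forfeiture sentence with payment pro-rated by completed assessment: Day 0, Day 1, Day 6 or discharge, and follow-up. State that stopping the device, or leaving because of discomfort or an adverse event, does not cancel payment for assessments completed before or after. A subject who stops the device can then still be paid for giving the Discharge and follow-up samples and questionnaires.

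In the same amendment, reconcile the withdrawal paragraph, the study-doctor removal paragraph and Table 2 on two points: whether stopping the device counts as withdrawal, and what happens to payment when the study doctor removes a subject. Add the payment points to Table 2 and match the consent wording. The change concerns payment only and sets no rule on when treatment should stop.

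The cost is a short amendment with IRB approval, partial payments to the few subjects who leave early, and some loss of the incentive to complete. Pro-rating does not settle whether assessments are sought from subjects who leave the study altogether, so the protocol should state that separately.
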